#### Study summary:

- Identify patients aged ≥ 2 years attending the Emergency Department with a significant acute asthma exacerbation (using criteria above).
- Begin steroids and initial protocolised standard bronchodilator therapy. Observe in ER and score PRAM hourly.
- Research coordinator is informed and provides parents and child with study information to read during the child's period of observation in the ED.
- A decision about study inclusion should be made 2 hours post-steroid administration in children with PRAM of 8 or more.
- Once admission decision has been made, child is eligible for the study. Obtain consent from the parents and assent from child where possible. If the child is too unstable, assent will be explained and collected when the child is capable.

• After consent, participants will be randomized to one of the three treatment arms in blocks of six, using consecutively numbered opaque envelopes stored in the ED.

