## Sample size calculation.

In order to have an impact on common practice, we would define a significant treatment effect as a 25% reduction in time to PRAM of 3. In order to demonstrate this effect with a power of 80% and a 5% chance of a type 1 error, we need an estimate of mean time to PRAM of 3 plus standard deviation from previous published work. Unfortunately, there is very little published information to act as a guide. The only published pediatric study that provides relevant data is a pilot study by Basnet et al.[17] Using only 10 patients in each arm, they showed BiPAP reduced time in ICU (48+/- 16 hrs vs. 36+/-14 hrs). They used a clinical score to guide management but it was different to the PRAM. If we take the higher of these standard deviations as a rough guide to the average ICU admission time and combine it with a power of 80% and type 1 error risk of 5%, we will need 26 patients in each arm to detect a 25% reduction in time to PRAM of 3. It must be emphasized that the shortage of relevant literature makes this only a rough estimate.

Statistical analysis.

Outcomes in the two treatment arms of the study (BiPAP and CPAP), will be compared to those in the control group (conventional acute paediatric asthma treatment). The principal end points will be analysed in the following ways:

1. Changes in asthma score over time.

The PRAM respiratory distres score is based on objective and subjective observations so the final values are non-parametric. Multiple comparisons over time, between treatment group and control, will be made with the Kruskal-Wallace test with Dunn's posthoc test.

2. Time to reach asthma score <3.

The value will be measured in hours after starting treatment so the values will be parametric. Comparison between treatment and control values will be made using t test. 3. Total number of pharmacological treatments per day.

The total number of drug treatments will be calculated for each 12 hour period. These are parametric values. Comparisons between control and treated group of repeat measures over time, will be made by analysis of variance with Tukey's post-hoc test. 4. Lung function tests.

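### Time to the PRAM threshold is compared by an unadjusted t test, although the PRAM score before randomisation is available and would probably give a small-to-moderate gain in precision

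*Combined protocol and SAP*

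**What the plan says.** The section on sample size sets its target on this endpoint: "we would define a significant treatment effect as a 25% reduction in time to PRAM of 3", "with a power of 80% and a 5% chance of a type 1 error". Item 2 of the statistical analysis then describes the endpoint and its test: "The value will be measured in hours after starting treatment so the values will be parametric", and "Comparison between treatment and control values will be made using t test". No covariate is mentioned there or in the other analysis items.

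The Study summary provides a baseline value. During initial treatment, staff are to "Observe in ER and score PRAM hourly". The next step is "A decision about study inclusion should be made 2 hours post-steroid administration in children with PRAM of 8 or more". Consent follows, and then "participants will be randomized to one of the three treatment arms in blocks of six". Neither the Study summary nor the Randomization section stratifies by PRAM or any other measure of severity.

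The plan calls no endpoint primary; it lists several principal ones. Time to the PRAM threshold is singled out here because the sample size is built on it.

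**The concern.** The outcome is the time a score takes to fall to a fixed level, and the starting value of that score is known for every child before allocation. A child who starts higher has further to fall, so part of the spread in the outcome should be explained by the baseline. A t test leaves that part in the error term, and the standard error is then larger than it need be.

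A chance difference between arms in starting severity also shifts the unadjusted estimate, in proportion to the correlation between baseline and outcome. Stratification does not limit such differences here. Because the trial is open, a decision to adjust made after an imbalance has been seen would carry little weight. The choice has to be written down beforehand.

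At stake is power in a trial with a thin margin, whose own sample size section calls its figure a rough estimate.

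**Working it through.** **Inputs from the documents.** The pilot study of ICU time cited under Sample size calculation gives 48 (SD 16) h against 36 (SD 14) h. The plan uses the larger SD, 16 h. A 25% reduction on 48 h is 0.25 × 48 = 12 h. Power is 80% and type 1 error 5%, taken here as two-sided because sidedness is not stated. The stated need is 26 per arm; the Overview of study design projects at least 30.

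**Input not in the documents.** r, the within-arm correlation of the last PRAM before randomisation with time to the threshold. It is assumed, over the range 0 to 0.5.

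**Step 1: the plan's own figure.** n per arm = 2 × [SD × (1.960 + 0.842) / 12]².
- SD 16 gives 27.9, so 28 (29 with the t distribution).
- The pooled SD, √((16² + 14²)/2) = 15.03, gives 25.6 with the t distribution, so 26.

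The stated 26 is therefore reproduced exactly with the pooled SD and to within two or three patients with SD 16. The difference does not affect this point.

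**Step 2: unadjusted power.** SE = 16 × √(2/30) = 4.13 h. The noncentral t distribution with 58 degrees of freedom gives 81.5%. At 26 per arm, SE = 4.44 h and power is 75.6%.

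**Step 3: adjusted power.** In a linear model the residual SD is 16 × √(1 − r²). Estimating the covariate costs one degree of freedom and raises the expected variance by the factor 1 + 1/(2n − 4), which is 1.018 at 30 per arm and 1.021 at 26. So SE = 16 × √(1 − r²) × √[(2/n) × (1 + 1/(2n − 4))], with 2n − 3 degrees of freedom. Each comparison with control is treated as a two-arm comparison.

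| r | Residual SD (h) | Power, 30 per arm | Power, 26 per arm |
|---|---|---|---|
| Unadjusted | 16.00 | 81.5% | 75.6% |
| 0 | 16.00 | 80.8% | 74.7% |
| 0.2 | 15.68 | 82.4% | 76.4% |
| 0.3 | 15.26 | 84.3% | 78.5% |
| 0.4 | 14.66 | 87.0% | 81.7% |
| 0.5 | 13.86 | 90.5% | 85.8% |

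In terms of variance, the break-even is where 1 − r² = (2n − 4)/(2n − 3): r of about 0.13 at 30 per arm and 0.14 at 26.

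**Step 4: which r is plausible.** If the PRAM level of 8 governs entry, the baseline range is narrowed and r falls. With an unrestricted correlation R and a baseline SD cut to a fraction u, r = R × u / √(1 − R² + R²u²). Taking R = 0.5 as an assumption:
- u = 0.4: 0.20/√0.79 = 0.23
- u = 0.7: 0.35/√0.8725 = 0.37 to 0.38

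At r = 0.23 and 0.38, adjusted power at 30 per arm is 82.9% and 86.4%. The gain is about 1.4 to 4.9 points.

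**Step 5: effect of imbalance.** The unadjusted estimate shifts by r × d × 16 h, where d is the difference in mean baseline PRAM in SD units. At 30 per arm the standard error of d is √(2/30) = 0.26.
- d = 0.25, r = 0.3: 1.2 h
- d = 0.5, r = 0.3: 2.4 h
- d = 0.5, r = 0.5: 4.0 h

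A d of 0.5 is nearly two standard errors (0.5/0.26 = 1.9), so 4.0 h is towards the extreme. The target effect is 12 h.

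**The case against.** The strongest defence is that nothing here is an error. Under randomisation the unadjusted comparison is unbiased by baseline severity, and its type 1 error already allows for chance imbalance. The benefit rests wholly on a correlation that the documents do not give, and the entry level probably lowers it. The SD and effect are themselves taken from ICU time in another study. All of this stands and limits the size of the claim. It does not remove the case for adjusting, because the possible loss is under one point of power and the value is already collected.

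A reader might infer more than the documents support:
- **That the t test is biased, or that an imbalance passes in full into the treatment effect.** It passes in proportion to r, as Step 5 shows.
- **That the trial gains patients at no cost, for example 30/(1 − 0.3²) = 33 or 30/(1 − 0.5²) = 40 effective patients per arm.** This leaves out the cost of estimating the covariate and the low values of r.
- **That the same gains apply to a Cox model.** The shrinking residual SD is a linear-model result. In a Cox model the standard error does not shrink in that way, and the adjusted hazard ratio is a different quantity from the unadjusted one.
- **That the covariate can simply be added to the analysis of PRAM over time.** That analysis is a Kruskal-Wallis test with Dunn's test, which takes no covariate.
- **That the plan names this its primary comparison.** It does not; the status is inferred from the sample size.

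**Conclusion.** The point holds as one of lost precision. The endpoint that sets the sample size is analysed without a baseline value that is already collected before randomisation and is structurally linked to the outcome. No other part of the plan makes up for this.

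At 30 per arm, adjustment moves power from 81.5% to between 80.8% (r = 0) and 90.5% (r = 0.5). With a narrowed baseline range, a gain of roughly 1 to 5 points is the more realistic expectation. This assumes a linear model, SD 16 h, a 12 h effect and two-sided 5%. The observation that no covariate is planned is certain; the size of the gain is not. The change is worth making, but the trial's validity does not depend on it.

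**What to change.** In item 2, replace the t test with a prespecified linear model of time to the PRAM threshold on treatment arm and the last PRAM recorded before randomisation, and report each treatment arm against control with a confidence interval. Say that the baseline is the last hourly score before the envelope is opened.

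If the endpoint is instead analysed as time-to-event, for example because some children leave the study or go to ICU before reaching the threshold, include the same covariate in that model. The power figures above should not then be quoted.

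The cost is a short change to the analysis text, one degree of freedom, and under one point of power if baseline PRAM turns out not to be prognostic. No new data are needed. Adjusting the analysis of PRAM over time would mean replacing its method, and is not part of this change.

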However, a minority will not respond adequately to such management and require adjunctive medications, usually requiring admission to the ward, and sometimes to the ICU. Medical treatments commonly used in addition to beta agonists, include intravenous magnesium sulfate, inhaled anticholinergics and aminophylline. The evidence base for the efficacy of such treatments is limited and inconsistent, and adverse side effects are common [7].

There is growing evidence that positive airway pressure delivered by a non-invasive face mask, can reduce airway obstruction and also improve ventilation-perfusion mismatch. The resulting decrease in respiratory work and reduced need for added oxygen, shortens hospital stay and minimizes exposure to multiple medications [8]. In recent years the use of non-invasive positive pressure ventilation for management of a range of acute respiratory pathologies has become increasingly common. Results from studies in this area are encouraging, however most studies to date have been small and retrospective [9]. There is very little prospective controlled research to guide clinical practice concerning non-invasive ventilation in asthma. In view of the limited information available in the published literature, we believe that a prospective controlled trial of the value of BiPAP in acute asthma would provide a valuable evidence base to guide the management of this common clinical problem.

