## **Research Methods:**

## Overview of study design:

The aim of the study is to determine if the use of NIV, for children admitted to hospital with an acute exacerbation of asthma, reduces their work of breathing, need for adjunctive medication, length of hospital stay, and need for intubation and mechanical ventilation. Study design will be prospective, randomized and controlled. The tightly fitting face mask necessary for NIV makes it impossible to make this a blinded study.

The principal enrollment criteria will be children over 2 years of age presenting to the ER with acute asthma. After diagnosis, all children are treated with standard therapy (systemic steroids plus 3 doses of inhaled salbutamol and 1 dose of inhaled ipratropium over a 1 hour period then hourly salbutamol). The principal decision between discharge track and admission track will be made at 2 hours after first steroid dose. Admission criteria are based on sequential PRAM scores.

After initial asthma treatment and observation in the emergency room, to determine which patients can be discharged home, those who need admission will be asked to join the study, then consented and randomized. There will be three treatment groups:

- BiPAP: standard steroid dose, hourly salbutamol and BiPAP at 15/5 cm H2O by face mask with rate 10 to 15/min, oxygen as needed.
- CPAP: standard steroid dose, hourly salbutamol and 8 to 10 cm H2O constant pressure by face mask, oxygen as needed.
- Conventional therapy: standard steroid dose plus hourly nebulized salbutamol, nebulized ipratropium q 6 hrly, magnesium sulphate 50 mg/kg IV (4 doses q 6 hrly), loading dose of aminophylline 6 mg/kg IV if no progress, oxygen as needed.

All children will be admitted to a small 3 bed respiratory unit. They will be closely monitored and objectively scored every 4 hours using the PRAM asthma clinical severity score (Pediatric Respiratory Assessment Measure)[18]. End points will be: time to reach room air, time to reach PRAM score <3, numbers requiring intubation and mechanical ventilation and medication use. Those children older than 5 or 6 yrs, will also perform lung function tests twice daily. Projected patient enrollment will be at least 30 in each arm. Estimated study duration is 6 months.

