## Management of treatment groups:

Participants will be randomized into one of three treatment arms – BiPAP, CPAP, conventional therapy. In addition to standard therapy, the three treatments will consist of:

- BiPAP group (Trilogy device) to be started in the ER after randomization, pressures 16/5 cm H2O, with rate of 10 to 15 / minute plus hourly salbutamol.
- CPAP group (Trilogy device) to be started in ER after randomization. Starting pressure 8 cm H2O, increased to 10 cm H2O if no clinical response and hourly salbutamol.
- Conventional therapy, hourly nebulized salbutamol, nebulized ipratropium q 6 hrly, magnesium sulphate 50 mg/kg IV (4 doses q 6 hrly), loading dose of aminophylline 6 mg/kg IV if no progress.

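### The tested drug count includes ipratropium and magnesium scheduled only in the control arm, so a control-versus-NIV difference cannot show reduced need for adjunctive medication

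*Combined protocol and SAP*

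**What the plan says.** Hypothesis and aims and the Overview of study design both give a reduced need for adjunctive medication as an aim. The Study background says which drugs these are: "Medical treatments commonly used in addition to beta agonists, include intravenous magnesium sulfate, inhaled anticholinergics and aminophylline".

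Measured Outcomes lists total medication use per 12 h. Statistical analysis (under Sample size calculation) treats it as a principal end point in item 3: "The total number of drug treatments will be calculated for each 12 hour period". The test is: "Comparisons between control and treated group of repeat measures over time, will be made by analysis of variance", followed by Tukey's post-hoc test. No drug is excluded from the count. No other analysis of drug use is listed.

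The drug schedules differ by arm.

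- **Control** (Management of treatment groups): "Conventional therapy, hourly nebulized salbutamol, nebulized ipratropium q 6 hrly, magnesium sulphate 50 mg/kg IV (4 doses q 6 hrly"), plus a "loading dose of aminophylline 6 mg/kg IV if no progress".
- **NIV arms:** the Overview has "BiPAP: standard steroid dose, hourly salbutamol and BiPAP at 15/5 cm" H2O. CPAP likewise has the steroid and hourly salbutamol. Neither NIV arm lists ipratropium, magnesium or aminophylline.
- **All arms** (General care for all three groups): once-daily dexamethasone for four days, and ordinary medical review with ICU admission if a child deteriorates.

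Every child also receives one ipratropium dose in the ER, but that is before randomisation and equal across arms.

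**The concern.** The three drugs that the Study background names as additions to beta agonists are the same three that the protocol writes into the conventional arm alone. Two of them, ipratropium and magnesium, are given there by the clock and not in response to the child's condition. A total that includes them is therefore higher in control by allocation, before any effect of NIV on the child.

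Because this is the only listed analysis of drug use, it is the only one that could be offered for the adjunct-need aim. A significant control-versus-NIV result could be reported as reduced need when it reflects the assigned schedules. The trial is also open label (the mask "makes it impossible to make this a blinded study"), so blinding gives no protection to the drugs given at the clinician's discretion.

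**Working it through.** **The plan's own figure.** The plan gives no mean, SD or power for the drug count. Its only sample-size figure is 26 per arm for time to PRAM of 3. With a difference of 0.25 × 48 = 12 h, SD 16, two-sided 5% and 80% power, n = 2 × (1.960 + 0.842)² × 16² / 12² ≈ 28. With the pooled SD of 15.03 it is 25. The stated 26 is reproduced to within two patients and is not at issue. The check below uses 26 and the projected enrolment of 30 per arm as group sizes only.

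**Step 1: scheduled treatments per 12 h.** Each dose counts as one treatment, and periods run from randomisation. The admission decision "will be made at 2 hours after first steroid dose", so the first dexamethasone dose comes before randomisation and the next daily doses fall in periods 2 and 4.

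| Period | Salbutamol | Ipratropium (control) | Magnesium (control) | Dexamethasone | Control | NIV | Gap |
|---|---|---|---|---|---|---|---|
| 0–12 h | 12 | 2 | 2 | 0 | 16 | 12 | 4 |
| 12–24 h | 12 | 2 | 2 | 1 | 17 | 13 | 4 |
| 24–36 h | 12 | 2 | 0 | 0 | 14 | 12 | 2 |
| 36–48 h | 12 | 2 | 0 | 1 | 15 | 13 | 2 |

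Over the first 24 h: 16 + 17 = 33 against 12 + 13 = 25, and 33/25 = 1.32. Conditional aminophylline would add to the control total and is left out. BiPAP and CPAP share one drug schedule, so their gap is 0.

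**Step 2: how often the gap alone is significant.** This takes one 12 h period and one control-versus-NIV pair. Tukey with three groups and 30 per arm has df = 87 and q = 3.372, so the critical t is 3.372/√2 = 2.384. The non-centrality is gap / (SD × √(2/30)); for a gap of 4 and SD 4 this is 4 / (4 × 0.2582) = 3.87. With 26 per arm, df = 75 and q = 3.382. The documents give no SD, so the SDs are assumed and ranged.

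| Scenario | SD 3 | SD 4 | SD 5 | SD 6 | SD 8 |
|---|---|---|---|---|---|
| Gap 4, n = 30 | 0.997 | 0.929 | 0.761 | 0.580 | 0.332 |
| Gap 2, n = 30 | 0.580 | 0.332 | 0.208 | 0.143 | 0.083 |
| Gap 4, n = 26 | 0.991 | 0.885 | 0.689 | 0.508 | 0.284 |

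With equal schedules (gap 0) the rate is 0.019 per pair. An unadjusted two-sample t-test would give higher rates: 0.968 and 0.861 at SD 4 and 5 for a gap of 4 with 30 per arm.

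**Step 3: allowing for rescue in the NIV arms.** Suppose a fraction f of NIV children receive the same 4 treatments per 12 h as rescue. The mean gap is then 4 × (1 − f), and the extra variance is included (simulation, 40,000 trials, n = 30).

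| f | Mean gap | SD 3 | SD 4 | SD 5 | SD 6 | SD 8 |
|---|---|---|---|---|---|---|
| 0.25 | 3 | 0.868 | 0.640 | 0.445 | 0.317 | 0.174 |
| 0.50 | 2 | 0.454 | 0.279 | 0.186 | 0.131 | 0.079 |

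At f = 1 the rate returns to about 0.02.

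**The case against.** The strongest reply is that the total is a proper outcome for a comparison of strategies. The Study background argues that NIV spares children exposure to several drugs, and no section says item 3 will be read as need. Read beside time to PRAM of 3 and ICU transfer, equal recovery without the adjuncts would bear on whether they were needed. This stands as a defence of the total as a description of exposure. It does not make the test of the total evidence of need, and the plan states a need aim with no other drug analysis to serve it.

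Second, the count is not fixed by schedule. NIV children who deteriorate may receive further drugs, and Criteria for study termination mentions sedation for mask tolerance. Both could narrow the gap. This is true, and it is why the rates above are not false-positive rates for an inert NIV. But rescue only dilutes the built-in gap; it does not turn doses given by the clock into a measure of need.

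Third, the size is illustrative. The SDs are assumed. The calculation covers one period, not the planned repeated-measures analysis. The unit is also unclear: the item heading refers to a day and its text to 12 h, and neither says whether doses or distinct drugs are counted. All of this stands. If distinct drugs are counted, control is still higher by 2 while magnesium runs and by 1 while ipratropium alone continues, but the printed rates then do not apply.

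Fourth, unscheduled drugs might seem the better basis for a need comparison. They would also be asymmetric, because control children already receive the adjuncts by schedule.

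**Conclusion.** The concern holds. As written, item 3 builds in a control-versus-NIV difference by allocation: 4 scheduled treatments per 12 h in the first 24 h and 2 per 12 h thereafter while dosing continues. These gaps assume that each dose is counted, schedules run in full and clinical courses are equal. Under those assumptions and 30 per arm, a gap of 4 is significant in 33% to 99.7% of trials over assumed SDs of 8 down to 3, against about 2% with equal schedules. Rescue in half of the NIV children lowers the range to 8% to 45%.

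That the test cannot support a claim of reduced need follows from the schedules and rests on no assumed SD. The damage is confined to that claim. Time to PRAM of 3, the sample size and BiPAP versus CPAP are not affected.

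**What to change.** In Measured Outcomes and in item 3 of the Statistical analysis:

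1. Report total drug treatments by arm as exposure under the assigned strategy. Separate arm-assigned drugs from unscheduled drugs, with conditional aminophylline in control and sedation for mask tolerance each on its own line. State whether doses or distinct drugs are counted.
2. State that a control-versus-NIV difference in the total will not be interpreted as reduced need for adjunctive medication. BiPAP versus CPAP may still be compared.
3. Limit any control-versus-NIV comparison of drug use to drugs scheduled identically in all arms, for example salbutamol treatments actually given. Show it as an estimate with a 95% CI, labelled open label, and describe it as bronchodilator use and not adjunct need. Salbutamol is already part of the recorded total, so no new endpoint is added.

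**Cost.** A scheduled/unscheduled flag on the drug record, revised wording, and a smaller apparent benefit. The adjunct-need aim is no longer tested between control and NIV. The salbutamol estimate is only moderately precise: with 30 per arm the half-width is t(0.975, 58) × SD × √(2/30), or 1.55, 2.07, 2.58, 3.10 and 4.13 treatments per 12 h at assumed SDs of 3, 4, 5, 6 and 8. It carries no information if every child receives all 12 scheduled doses. Treatments and sample size do not change.

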#### Measured Outcomes:

- Length of time to reach a PRAM score of  $\leq 3$
- Time to room air.
- Total medication use per 12 hr period.
- Numbers failing treatment and transferred to ICU.
- Numbers in each group requiring hospital readmission within 48 hours of discharge
- Time to reach FEV1 >80% predicted in those children able to perform PFTs.

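### Medication use is counted per 12-hour period with no per-child total and no rule for periods after recovery, discharge or ICU transfer; if those periods are missing, less total exposure can go undetected and later periods are selective

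*Combined protocol and SAP*

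**What the plan says.** The Measured Outcomes list gives the end point as "Total medication use per 12 hr period". Statistical analysis, item 3, is headed "Total number of pharmacological treatments per day", but the text beneath uses another unit: "The total number of drug treatments will be calculated for each 12 hour period". The method is: "Comparisons between control and treated group of repeat measures over time, will be made by analysis of variance with Tukey's post-hoc test". Item 3 is one of the four analyses given for the principal end points.

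The purpose is set out elsewhere. The Study background says that less respiratory work and less need for oxygen "shortens hospital stay and minimizes exposure to multiple medications". The Overview of study design asks whether NIV "reduces their work of breathing, need for adjunctive medication, length of hospital stay, and need for intubation and mechanical ventilation".

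Under Management of treatment groups, the BiPAP arm is ventilated "with rate of 10 to 15 / minute plus hourly salbutamol", and the CPAP and conventional arms also have salbutamol every hour. Only the conventional arm is scheduled to receive "nebulized ipratropium q 6 hrly, magnesium sulphate 50 mg/kg IV (4 doses q 6 hrly"), with aminophylline if there is no progress. No rule for stepping salbutamol down is given.

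Nowhere do the documents say whether a 12-hour period after recovery, discharge or ICU transfer counts as zero, as missing or as a partial period. Criteria for study termination end participation at signs of impending respiratory failure, so the dose record may also stop early for the sickest children.

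**The concern.** If NIV works as the plan supposes, much of the drug saving comes from a shorter course, that is, from fewer 12-hour periods. For a drug on the same clock in every arm, a count per period among children still being treated does not register that saving.

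The second problem is selection. A repeated-measures analysis needs a value for each child in each period. If children who have left have no value, each later comparison is restricted to slow recoverers, and the restriction depends on an outcome that treatment is meant to change. A complete-case repeated-measures ANOVA would go further and drop early leavers from every period.

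The trial is also unblinded. A scoring rule left unwritten can be settled after the data have been seen, and the working below shows that the answer depends on it.

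**Working it through.** **The plan's own figure.** No figure is given for the medication end point. The only calculated figure is 26 per arm for time to PRAM 3. With a 12 h difference, SD 16 h, two-sided 5% and 80% power, 2 × (1.96 + 0.84)² × 16² / 12² = 27.9, so 28, close to the stated 26. That figure does not depend on this end point.

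**Scheduled counts per full 12 h** (from Management of treatment groups; steroid and aminophylline left out)

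- Salbutamol: 12 / 1 = 12 in every arm.
- Control only: ipratropium 12 / 6 = 2, and magnesium 12 / 6 = 2 for the first 24 h (four doses).
- Control: 12 + 2 + 2 = 16 in each of the first two periods, then 12 + 2 = 14. NIV: 12 throughout.

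**Children remaining.** Assumptions: the pilot ICU times in the sample size section (48 ± 16 h v 36 ± 14 h) stand in for time on treatment, and times are gamma-distributed with shape (mean/SD)² and scale SD²/mean. Control has shape 9.00 and scale 5.33 h; NIV has shape 6.61 and scale 5.44 h.

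| Time | Control | NIV | Of 30 per arm |
|---|---|---|---|
| 24 h | 96% | 80% | 29 v 24 |
| 36 h | 76% | 45% | 23 v 13 |
| 48 h | 46% | 18% | 14 v 5 |
| 60 h | 21% | 6% | 6 v 2 |

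**Effect of the unwritten rule: salbutamol only, hourly until treatment ends.** Mean doses, control v NIV. The zero-scored mean is the integral over the period of the fraction still on treatment.

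| Period | Full periods only | Partial last period counted as it stands | Zero after leaving |
|---|---|---|---|
| 24–36 h | 12 v 12 | 10.9 v 9.4 | 10.5 v 7.5 |
| 36–48 h | 12 v 12 | 9.6 v 8.1 | 7.3 v 3.6 |
| 48–60 h | 12 v 12 | 8.5 v 7.3 | 3.9 v 1.3 |

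The same records give no difference, a modest one or a large one, according to the rule.

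**Total per child.** Summing the zero-scored means to 96 h gives 47.9 v 36.0 doses, and 1 − 36.0/47.9 = 25% lower. To 72 h, the same integral gives 47.2 v 35.9, 24% lower. In simulation (30 per arm, Poisson counts with mean equal to hours on treatment, two-sided 5%), a t test on the whole-course total rejects in about 78 to 81% of trials. A t test or rank test on the 72 h total rejects in about 80%. A test on each child's average count per 12 h on treatment rejects in about 5 to 6%, the nominal level. That last result is built in, because both arms are given the same hourly rate. It shows what the rate cannot register and does not predict the trial's result.

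**Pooled count.** Adding the control-only ipratropium and magnesium gives about 59.8 v 36.0, 40% lower with NIV. Of the difference of 23.8, 59.8 − 47.9 = 11.9 is the scheduled control-only drugs, about half.

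**The case against.** The strongest reply is that the defect depends on a rule the plan never states. A reader might infer that counting is confined to the hospital stay, since the only outcome listed after discharge is readmission within 48 hours. The text does not say so. If discharged children score zero, the 12-hour unit does no harm: the table shows 7.3 v 3.6 doses at 36–48 h.

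A reader might also infer that the planned analysis would show no reduction in drug use. The documents do not support that either. Item 3 counts all drug treatments, and the control arm's schedule alone puts the counts at 16 v 12 and then 14 v 12 before any effect of NIV on the illness. Partial last periods, or stepping salbutamol down during recovery, would also lower the count. These points stand, and the concern is therefore conditional. They do not rescue the end point: a difference created by the assigned schedule is not evidence of faster recovery.

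A further reply is that the stated aim is less adjunctive medication, and that a salbutamol total largely repeats duration, which time to PRAM and time to room air already measure. This has force and is a reason to report by drug class. It does not supply the missing scoring rule, and the Study background does claim less exposure to multiple medications.

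**Conclusion.** The concern holds in conditional form. The end point has no per-child total, no common window and no rule for periods after recovery, discharge or ICU transfer. If those periods are missing, the analysis can miss a reduction of about 25% in total salbutamol exposure, and by 48 h it compares about 14 of 30 control children with about 5 of 30 NIV children. Any difference in the pooled count mixes recovery with the 2 to 4 scheduled doses per 12 h that only the control arm receives.

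The sizes rest on ICU time standing in for time on treatment, gamma-shaped times, and constant hourly salbutamol until treatment ends. The absence of a rule, and the mismatch between the daily heading and the 12-hour text, need no assumption. The sample size is unaffected. The point should be settled before analysis because it concerns a principal end point of an open trial.

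**What to change.** Replace item 3 with one number per child:

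- **Outcome:** treatments given from randomisation to one fixed horizon (for example 72 h), counted as zero after discharge and with ICU doses included. State that zero refers to inpatient treatment, and say how doses during a readmission within the horizon are counted.
- **Drug class:** analyse salbutamol separately from the drugs scheduled only in the control arm, and present any pooled total as reflecting the assigned regimen as well as recovery.
- **Comparison:** each NIV arm against control, in all randomised children, by a rank test or a count regression, with the choice fixed in advance.
- **12-hour counts:** keep them as a descriptive plot, with the number of children contributing to each period shown.
- **Unit:** reconcile the daily heading with the 12-hour text.

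The cost is small: SAP wording, and a statement that dose recording continues to the horizon after ICU transfer or the end of study participation. That is a data collection change only. No extra patients are needed.
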